11.1.3 Expectedness

Adverse events can be 'Expected' or 'Unexpected.'

11.1.3.1 Expected adverse event

Expected adverse events are those that have been previously identified as resulting from administration of the agent. For the purposes of this study, an adverse event is considered expected when it appears in the current adverse event list, the Investigator's Brochure, the package insert or is included in the informed consent document as a potential risk.

Refer to Section 6.1 for a listing of expected adverse events associated with the study agent(s).

11.1.3.2 Unexpected adverse event

For the purposes of this study, an adverse event is considered unexpected when it varies in nature, intensity or frequency from information provided in the current adverse event list, the Investigator's Brochure, the package insert or when it is not included in the informed consent document as a potential risk.

11.1.4 Attribution

Attribution is the relationship between an adverse event or serious adverse event and the study treatment. Attribution will be assigned as follows:

- Definite – The AE is clearly related to the study treatment.
- Probable – The AE is likely related to the study treatment.

- Possible – The AE may be related to the study treatment.
- Unlikely - The AE is doubtfully related to the study treatment.
- Unrelated - The AE is clearly NOT related to the study treatment.

11.2 Procedures for AE and SAE Recording and Reporting

Reporting Participating investigators will assess the occurrence of AEs and SAEs at all participant evaluation time points during the study.

All AEs and SAEs whether reported by the participant, discovered during questioning, directly observed, or detected by physical examination, laboratory test or other means, will be recorded in the participant's medical record and on the appropriate study-specific case report forms.

The descriptions and grading scales found in the CTEP Active Version of the NCI Common Terminology Criteria for Adverse Events (CTCAE) will be utilized for AE reporting. The CTEP Active Version of the CTCAE is identified and located on the CTEP website at:

http://ctep.cancer.gov/protocolDevelopment/electronic_applications/ctc.htm.

All appropriate treatment areas should have access to a copy of the CTEP Active Version of CTCAE.

11.3 Reporting Requirements

For multi-site trials where a DF/HCC investigator is serving as the principal investigator, each participating investigator is required to abide by the reporting requirements set by the DF/HCC. The study must be conducted in compliance with FDA regulations, local safety reporting requirements, and reporting requirements of the principal investigator.

Each investigative site will be responsible to report SAEs that occur at that institution to their respective IRB. It is the responsibility of each participating investigator to report serious adverse events to the study sponsor and/or others as described below.

11.4 Reporting to the Study Sponsor

11.4.1 Serious Adverse Event Reporting

All serious adverse events that occur after the initial dose of study treatment, during treatment, or within 30 days of the last dose of treatment must be reported to the DF/HCC Overall Principal Investigator on the local institutional SAE form. This includes events meeting the criteria outlined in Section 11.1.2, as well as the following:

- Grade 2 (moderate) and Grade 3 (severe) events that are unexpected and at least possibly related/associated with the intervention.
- All Grade 4 (life-threatening or disabling) events that are unexpected AND not specifically listed in the protocol as not requiring reporting.
- All Grade 5 (fatal) events while the participant is enrolled and actively participating in the trial OR when the event occurs within 30 days of the last study intervention.

Note: If the participant is in long term follow up, report the death at the time of continuing review.

Participating investigators must report each serious adverse event to the DF/HCC Overall Principal Investigator within 24 hours of learning of the occurrence. In the event that the participating investigator does not become aware of the serious adverse event immediately (e.g., participant sought treatment elsewhere), the participating investigator is to report the event within 24 hours after learning of it and document the time of his or

her first awareness of the adverse event. Report serious adverse events by telephone, email or facsimile to:

[name].

Within the following 48 hours, the participating investigator must provide follow-up information on the serious adverse event. Follow-up information should describe whether the event has resolved or continues, if and how the event was treated, and whether the participant will continue or discontinue study participation.

11.4.2 Non-Serious Adverse Event Reporting

Non-serious adverse events will be reported to the DF/HCC Overall Principal Investigator on the toxicity Case Report Forms.

11.5 Reporting to the Institutional Review Board (IRB)

Investigative sites within DF/HCC will report all serious adverse events directly to the DFCI Office for Human Research Studies (OHRS).

Other investigative sites should report serious adverse events to their respective IRB according to the local IRB's policies and procedures in reporting adverse events. A copy of the submitted institutional SAE form should be forwarded to:

[name].

The DF/HCC Principal Investigator will submit SAE reports from outside institutions to the DFCI Office for Human Research Studies (OHRS) according to DFCI IRB policies and procedures in reporting adverse events.

11.6 Reporting to Hospital Risk Management

Participating investigators will report to their local Risk Management office any subject safety reports or sentinel events that require reporting according to institutional policy.

11.7 Monitoring of Adverse Events and Period of Observation

All adverse events, both serious and non-serious, and deaths that are encountered from initiation of study intervention, throughout the study, and within 30 days of the last study intervention should be followed to their resolution, or until the participating investigator assesses them as stable, or the participating investigator determines the event to be irreversible, or the participant is lost to follow-up. The presence and resolution of AEs and SAEs (with dates) should be documented on the appropriate case report form and recorded in the participant's medical record to facilitate source data verification.

For some SAEs, the study sponsor or designee may follow-up by telephone, fax, and/or monitoring visit to obtain additional case details deemed necessary to appropriately evaluate the SAE report (e.g., hospital discharge summary, consultant report, or autopsy report).

Participants should be instructed to report any serious post-study event(s) that might reasonably be related to participation in this study. Participating investigators should notify the DF/HCC Overall Principal Investigator and their respective IRB of any unanticipated death or adverse event occurring after a participant has discontinued or terminated study participation that may reasonably be related to the study.

12 DATA AND SAFETY MONITORING

12.1 Data Reporting

12.1.1 Method

The ODQ will collect, manage, and monitor data for this study.

12.1.2 Data Submission

The schedule for completion and submission of case report forms (paper or electronic) to the ODQ is as follows:

Form	Submission Timeline
Eligibility Checklist	Complete prior to registration with QACT
On Study Form	Within 14 days of registration
Lab Form	Within 14 days of registration; and within 14 days of protocol defined laboratory assessment
Tumor Measurement/Staging Form	Within 14 days of registration; and within 14 days of protocol defined restaging assessment
Chemotherapy Treatment Form	Within 10 days of the last day of the cycle of neoadjuvant FOLFIRINOX; within 10 days of the last cycle of adjuvant chemotherapy, if any
Chemoradiation Treatment Form	Within 10 days of completion of neoadjuvant combined capecitabine and proton radiation
Toxicity/Adverse Event Report Form	Every two weeks during neoadjuvant FOLFIRINOX; weekly during chemoradiation; and within 14 days of protocol defined follow up visit
PRO's	Within 14 days of completion
Surgery/Pathology Form	Within 14 days of surgery
Off Treatment/Off Study Form	Within 14 days of completing treatment or being taken off study for any reason

Follow up/Survival Form	Within 14 days of the protocol defined follow up visit date
-------------------------	---

12.2 Safety Meetings

The DF/HCC Data and Safety Monitoring Committee (DSMC) will review and monitor toxicity and accrual data from this trial. The committee is composed of clinical specialists with experience in oncology and who have no direct relationship with the study. Information that raises any questions about participant safety will be addressed with the Principal Investigator and study team.

The DSMC will meet as required to review toxicity and accrual data. Information to be provided to the committee may include: up-to-date participant accrual; current dose level information; DLT information; all grade 2 or higher unexpected adverse events that have been reported; summary of all deaths occurring within 30 days for Phase I or II protocols; for gene transfer protocols, summary of all deaths while being treated and during active follow-up; any response information; audit results, and a summary provided by the study team. Other information (e.g. scans, laboratory values) will be provided upon request.

12.3 Monitoring

Involvement in this study as a participating investigator implies acceptance of potential audits or inspections, including source data verification, by representatives designated by the DF/HCC Overall Principal Investigator (or Protocol Chair) or DF/HCC. The purpose of these audits or inspections is to examine study-related activities and documents to determine whether these activities were conducted and data were recorded, analyzed, and accurately reported in accordance with the protocol,

institutional policy, Good Clinical Practice (GCP), and any applicable regulatory requirements.

All data will be monitored for timeliness of submission, completeness, and adherence to protocol requirements. Monitoring will begin at the time of participant registration and will continue during protocol performance and completion.

13 REGULATORY CONSIDERATIONS

13.1 Protocol Review and Amendments

This protocol, the proposed informed consent and all forms of participant information related to the study (e.g., advertisements used to recruit participants) and any other necessary documents must be submitted, reviewed and approved by a properly constituted IRB governing each study location.

Any changes made to the protocol must be submitted as amendments and must be approved by the IRB prior to implementation. Any changes in study conduct must be reported to the IRB. The DF/HCC Overall Principal Investigator (or Protocol Chair) will disseminate protocol amendment information to all participating investigators.

All decisions of the IRB concerning the conduct of the study must be made in writing.

13.2 Informed Consent

All participants must be provided a consent form describing this study and providing sufficient information for participants to make an informed decision about their participation in this study. The formal consent of a participant, using the IRB approved consent form, must be obtained before the participant is involved in any study-related procedure. The consent form must be signed and

dated by the participant or the participant's legally authorized representative, and by the person obtaining the consent. The participant must be given a copy of the signed and dated consent document. The original signed copy of the consent document must be retained in the medical record or research file.

13.3 Ethics and Good Clinical Practice (GCP)

This study is to be conducted according to the following considerations, which represent good and sound research practice:

- E6 Good Clinical Practice: Consolidated Guidance
www.fda.gov/downloads/RegulatoryInformation/Guidances/UCM129515.pdf
- US Code of Federal Regulations (CFR) governing clinical study conduct and ethical principles that have their origin in the Declaration of Helsinki
 - Title 21 Part 11 – Electronic Records; Electronic Signatures
www.access.gpo.gov/nara/cfr/waisidx_02/21cfr11_02.html
 - Title 21 Part 50 – Protection of Human Subjects
www.access.gpo.gov/nara/cfr/waisidx_02/21cfr50_02.html
 - Title 21 Part 54 – Financial Disclosure by Clinical Investigators
www.access.gpo.gov/nara/cfr/waisidx_02/21cfr54_02.html
 - Title 21 Part 56 – Institutional Review Boards
www.access.gpo.gov/nara/cfr/waisidx_02/21cfr56_02.html
 - Title 21 Part 312 – Investigational New Drug Application
www.access.gpo.gov/nara/cfr/waisidx_02/21cfr312_02.html
- State laws
- DF/HCC research policies and procedures
<http://www.dfhcc.harvard.edu/clinical-research-support/clinical-research-unit-cru/policies-and-procedures/>

It is understood that deviations from the protocol should be avoided, except when necessary to eliminate an immediate hazard to a research participant. In such case, the deviation must be reported to the IRB according to the local reporting policy.

13.4 Study Documentation

The investigator must prepare and maintain adequate and accurate case histories designed to record all observations and other data pertinent to the study for each research participant. This information enables the study to be fully documented and the study data to be subsequently verified.

Original source documents supporting entries in the case report forms include but are not limited to hospital records, clinical charts, laboratory and pharmacy records, recorded data from automated instruments, microfiches, photographic negatives, microfilm or magnetic media, and/or x-rays.

13.5 Records Retention

All study-related documents must be retained for the maximum period required by applicable federal regulations and guidelines or institutional policies.

14 STATISTICAL CONSIDERATIONS

14.1 Study Design/Endpoints

This is a single-arm, phase II study to investigate the preoperative administration of FOLFIRINOX chemotherapy and accelerated short-course radiation therapy in patients with borderline-resectable adenocarcinoma of the pancreas.

The primary endpoint of this study is R0 resection rate determined by final pathology of the surgical specimen. The previously studied approach involved four months of induction gemcitabine followed by six weeks of neoadjuvant 5-FU-based chemoradiation (50.4 Gy). Our internal data support a historical R0 resection rate of 20% for patients with resectable

disease who received induction chemoradiation (CRT) (8 of 40) or induction chemotherapy followed by chemoradiation (C-CRT) (6 of 30). In a retrospective surgical series at MGH, median tumor size was 29 mm for the CRT group and 35 mm for C-CRT group. Among patients considered 'borderline resectable' upfront (n = 24), 5 of 24 = 21% had eventual margin-negative resection (or 7 of 24 = 29%, if < 1 mm is considered as a negative margin / R0 resection).

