5.2.7 Other Modalities and Procedures

5.2.7.1 Surgery: Surgery will be performed one to four weeks after completion of capecitabine therapy. If surgery is delayed beyond four weeks after completion of capecitabine, the patient will be taken off study. At laparotomy, the liver and pancreas will be examined by palpation and inspection. In the absence of metastases, tumor mobilization and surgical resection will be performed. A pancreaticoduodenectomy (Whipple procedure) or distal pancreatectomy with standard lymphadenectomy will be done. This involves dissection up to the superior mesenteric artery, with skeletonization of the right lateral and anterior aspects of the vessels. Feeding jejunostomy and gastrostomy tubes may be placed at the discretion of the operating surgeon.

5.2.7.2 Pathology: Processing the specimen and pathology will be reported according to the AJCC Cancer Staging Manual, 6th Edition. Pancreatic transection margin, and the bile duct margin will be evaluated on frozen section. Recorded on permanent section will be: tumor size, degree of differentiation (well, moderate, poor), lymph node status, and margin status.

5.2.7.3 Chemotherapy: Patients may receive adjuvant chemotherapy after at the discretion of the treating investigator. If adjuvant chemotherapy is administered, at minimum, administration of FOLFIRINOX therapy will be contingent on patients meeting original inclusion criteria (lab parameters and performance status). Physicians may opt to provide FOLFOX or FOLFIRI in the postoperative setting, with the full FOLFIRINOX regimen administered only when the patient is able to tolerate this therapy. If there is evidence of progression, patients will be withdrawn

from the study and as per NCCN guidelines, proceed to second-line therapy (likely gemcitabine-based chemotherapy.) Appropriate dose reductions and modifications can be made at the discretion of the treating physician.

5.3 General Concomitant Medication and Supportive Care Guidelines:

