14.2 Sample Size/Accrual Rate

The accrual goal of 50 patients is projected to be enrolled over a total period of 4 years based on the observed rate of accrual during the first two years since the protocol was open to patient entry.

The preoperative protocol regimen will have demonstrated an improvement in efficacy if an R0 resection were achieved in at least 16 of 50 patients. The decision rule is associated with 90% power if preoperative FOLFIRINOX and short-course radiation were able to improve the R0 resection rate to 40%. In contrast, the probability of type 1 error is only 3% if the underlying rate of R0 resection were truly the same as the historical data of 20%. All protocol patients who begin the preoperative regimen will be included in the denominator for analysis of the R0 resection rate, including those who do not undergo surgery due to progression or other reasons.

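### Does the plan need to say whether a margin under 1 mm counts as R0 before its 16-of-50 rule can be trusted?

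*Combined protocol and SAP*

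**What the plan says.** Section 14.1 sets the endpoint: "The primary endpoint of this study is R0 resection rate determined by final pathology of the surgical specimen". It gives no margin width.

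The same section supplies the benchmark: "Our internal data support a historical R0 resection rate of 20% for patients with resectable" disease, from 8 of 40 and 6 of 30 patients under two earlier strategies. It does not say how margins were scored in those 70. For 24 patients judged borderline resectable at the outset, the main clause reads "5 of 24 = 21% had eventual margin-negative resection", with a bracketed alternative: "7 of 24 = 29%, if < 1 mm is considered as a negative margin / R0 resection".

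Section 14.2 declares efficacy at 16 or more R0 resections in 50, with 90% power at a true rate of 40%. It puts the error thus: "probability of type 1 error is only 3% if the underlying rate of R0 resection were truly the same as the historical data" of 20%.

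On pathology, section 5.2.7.2 says "Processing the specimen and pathology will be reported according to the AJCC Cancer Staging Manual, 6th Edition" and "Recorded on permanent section will be: tumor size, degree of differentiation (well, moderate, poor), lymph node status, and margin status". Section 10.1.2 defines pathological complete response but not R0. Note 2 to the study calendar (section 9) uses R0, R1 and R2 without defining them.

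**The concern.** The authors plainly knew that two R0 conventions exist. They show that the choice moves the rate by two patients in 24, or 8.3 percentage points, in the very disease category the trial enrols. Yet they do not say which convention applies to trial specimens, or to the 8/40 and 6/30 behind the null.

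R0 rate is the primary endpoint, 16 of 50 is the only efficacy rule, and the comparison is with a fixed historical 20%. With no concurrent arm, a difference in scoring between trial and benchmark would go straight into the conclusion. There is also little slack, because a small rise in the no-improvement rate takes the error past 5%. A convention settled only after the count is known could decide whether 16 is reached.

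**Working it through.** **Inputs.** From 14.1: null 20% (8/40 = 6/30 = 20%), and the borderline series at 5/24 = 20.8% or 7/24 = 29.2%. From 14.2: n = 50, cut-off 16, target 40%, stated error 3%, stated power 90%.

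**Formula.** P(X ≥ 16 | p) = Σ C(50, x) p^x (1 − p)^(50 − x), summed over x = 16 to 50.

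**Reproducing the plan.**
- p = 0.20: 0.0308, matching the stated 3%.
- p = 0.40: 0.9045, matching the stated 90%.

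**Using the borderline series as the true no-improvement rate, with the rule unchanged.**
- p = 5/24: 0.0433.
- p = 7/24: 0.3803.

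**When does scoring distort the test?** There are four combinations of trial scoring and null scoring.

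| Trial specimens | 20% null | Effect on type I error |
|---|---|---|
| Strict | Strict | 3.1%, as stated |
| Lenient | Lenient | 3.1%, as stated |
| Strict | Lenient | At or below 3.1%: strict scoring cannot raise the rate, so the test is conservative |
| Lenient | Strict | Above 3.1%, by an amount that depends on how many margins are under 1 mm |

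Only the last row does harm.

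**Size in that row.** Solving P(X ≥ 16 | p) = 0.05 gives p = 0.212, which is (0.212 − 0.20) × 50 = 0.6 patients on average. Solving for 0.10 gives p = 0.232, or 1.6 patients. Adding the historical reclassification share to the null gives 0.20 + 2/24 = 0.283 and an error of 0.331.

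That share rests on two patients. Its exact 95% interval (Clopper-Pearson, 2/24) is 1.0% to 27.0%. At the lower end p = 0.210 and the error is 4.7%. At the upper end p = 0.470 and the rule would be met 99% of the time. The data therefore say almost nothing about the size of the effect in the mismatch row. The 33% and 38% are illustrations of sensitivity and do not estimate this trial's error.

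**Which row does the text suggest?** Section 14.1 calls the 5/24 margin-negative in its main clause and brings in 29% only under an if. The null of 20% sits beside 21%, not 29%. The historical data are internal to the institution. Section 3.1.1 has its pathology department confirm the diagnosis, and section 5.2.6.2 has all radiation given there. A switch of convention between benchmark and trial is therefore less likely, though not excluded. The natural reading is the first row.

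**The case for a change.** The strongest reply is that the wording of 14.1 describes how historical patients were presented and sets no rule for trial specimens. The 70 patients behind the 20% carry no margin definition at all. The AJCC manual may supply one by reference, but it was not available to check. One sentence would end the doubt, and it would be better written before the R0 count is known than after.

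Most of that stands as a remark on drafting: the definition is absent, and the strict reading is inferred. It does not show that the planned test is wrong. The stated error fails only if lenient trial scoring meets a strict null, and no section indicates that.

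The obvious repairs also carry a risk. Section 14.2 bases its projection on the "observed rate of accrual during the first two years since the protocol was open to patient entry", so patients had been accruing for about two years. Writing in a strict rule would be harmless if it is already in use; otherwise it would redefine the primary endpoint mid-trial. Replacing the null with 29% whenever scoring is lenient is not right either. If 8/40 and 6/30 were scored leniently too, 20% remains the matching null and the 3% is correct. At n = 50, controlling the error against 7/24 would need 21 successes (error 3.6%) and would leave 44% power at 40%, a heavy price for a mismatch nobody has shown.

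**Conclusion.** No change to the plan follows. The gap is real but is one of missing detail. Under the natural reading of 14.1 the stated operating characteristics are right (error 3.1% at 20%, 4.3% at 5/24; power 90.4% at 40%), and the 3.1% at 20% holds whenever trial and null share a convention. Pathologists report margin status under a named staging manual. Analysts can apply the convention in use and state it with the result, as is ordinary in reporting an R0 rate.

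This rests on two assumptions that the document does not let one verify: that trial specimens are scored as the historical ones were, and that the convention is not chosen by looking at the running count. If trial scoring proved lenient and the 20% strict, the error would exceed 5% once the no-improvement rate passed 21.2%, and the 3% should not then be quoted.

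Two matters lie outside this point and are unaffected by it: the imprecision of a 24-patient series (exact 95% interval 7.1% to 42.2% for 5/24), and 14.1's description of the 20% as coming from resectable rather than borderline-resectable disease.
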